3.4 Duration of Treatment

In the absence of treatment delays due to adverse events (AEs), neoadjuvant study treatment may continue (up to 3 cycles depending on cohort) until:

- Disease progression which requires discontinuation of the study treatment;
- Inter-current illness that prevents further administration of treatment;
- Unacceptable adverse event(s);
- Participant decides to withdraw from the study;
- Significant participant non-compliance with protocol;
- If the participant meets an exclusion criterion (either newly developed or not previously; or, recognized) that precludes further study participation
- General or specific changes in the participant's condition render the participant unacceptable for further treatment in the judgment of the investigator.

3.5 Duration of Follow Up

Participants will be followed for 2 years after cystectomy, removal from study, or until death, whichever occurs first. Participants removed from study for unacceptable treatment related adverse event(s) will be followed until resolution or stabilization of all treatment related adverse events to Grade 2 or lower.

3.6 Primary Completion

It is expected that the study will reach primary completion about 14-19 months from the time Cohort B opens to accrual, accounting for 11-16 months to accrue all subjects to Cohort B, and another 3 months from enrollment of last patient to cystectomy.

3.7 Study Completion

It is expected that the study will reach full completion 41-46 months from the time Cohort B opens to accrual.

4 Study Drugs

4.1 Description, Supply and Storage

4.1.1 Atezolizumab

Classification

Atezolizumab is a human monoclonal antibody based on a human IgG1 framework containing heavy chain VHIII and light chain VκI subgroup sequences. The recombinant antibody consists of two heavy chains (448 amino acid residues each) and two light chains (214 amino acid residues each) with inter- and intra-chain disulfide bonds that are typical of IgG1 antibodies.

Atezolizumab incorporates an amino acid substitution (asparagine to alanine) at position 298 in the CH2 domain of each heavy chain resulting in a non-glycosylated antibody that has minimal binding to Fcγ receptors and, consequently, prevents Fc-effector function and depletion of cells expressing PD-L1 at expected concentrations in humans. Therefore, atezolizumab lacks the N-linked oligosaccharides typically observed on other CHO-derived monoclonal antibodies.

Mechanism of Action

Atezolizumab targets programmed death-ligand 1 (PD-L1) on antigen-presenting cells or tumor cells and prevents interaction with programmed death-1 (PD-1) receptor, which is an inhibitory receptor expressed on T cells. Atezolizumab also blocks the interaction between PD-L1 and B7.1. Interference of the PD-L1:PD-1 and PD-L1:B7.1 interactions may enhance the magnitude and quality of the tumor-specific T-cell response through increased T-cell priming, expansion, and/or effector function.

Pharmacokinetics and Metabolism

Serum Atezolizumab concentrations exhibited a biphasic disposition with an initial rapid distribution phase followed by a slow elimination phase. Atezolizumab exhibited nonlinear pharmacokinetics at doses < 1 mg/kg (i.e., 0.03–0.3 mg/kg), likely due to target-mediated CL at lower concentrations. Atezolizumab exhibited linear pharmacokinetics at doses ≥ 1 mg/kg. At

doses ≥ 1 mg/kg, the mean Cmax increased in a dose-proportional manner and was 26.0 $\mu\text{g}/\text{mL}$ for the 1-mg/kg dose group and 486 $\mu\text{g}/\text{mL}$ for the 20-mg/kg dose group. Similarly, at doses ≥ 1 mg/kg, the group mean AUC $0-\infty$ had a range of 340–6050 day \times $\mu\text{g}/\text{mL}$ for 1-mg/kg and 20-mg/kg dose group and was approximately dose proportional, as evidenced by similar CL across the dose range. The observed CL and Vss for Atezolizumab at doses ≥ 1 mg/kg are consistent with these of a typical IgG1 antibody in humans. The development of anti-therapeutic antibodies (ATAs) has been observed in patients in all dose cohorts and was associated with changes in pharmacokinetics for some patients in the lower dose cohorts (0.3, 1, and 3 mg/kg). Patients dosed at the 10-, 15-, and 20-mg/kg dose levels have maintained the expected target trough levels of drug despite the detection of ATAs. Accordingly, the development of detectable ATAs does not appear to have a clinically significant impact on pharmacokinetics for doses from 10 to 20 mg/kg. To date, no relationship between the development of measurable ATAs and safety or efficacy has been observed.

The expected metabolic products of proteins and peptides, including IgG1 monoclonal antibodies such as atezolizumab, are small peptides and individual amino acids. Cytochrome P450 enzymes as well as conjugation/glucuronidation reactions are not involved in the metabolism of Atezolizumab.

Contraindications

Atezolizumab is contraindicated for patients with the following:

- History of severe allergic anaphylactic reactions to chimeric, human or humanized antibodies, or fusion proteins
- Known hypersensitivity to CHO cell products or any component of the atezolizumab formulation.

As with all investigational products, unknown side effects may occur. Patients should be monitored closely throughout their participation in clinical studies of Atezolizumab.

Availability

The atezolizumab drug product is provided in a single-use, 20-mL USP/Ph. Eur. Type 1 glass vial as a colorless to slightly yellow, sterile, preservative-free clear liquid solution intended for IV administration. The vial is designed to deliver 20 mL (1200 mg) of Atezolizumab solution but may contain more than the stated volume to enable delivery of the entire 20 mL volume. The Atezolizumab drug product is formulated as 60 mg/mL atezolizumab in 20 mM histidine acetate, 120 mM sucrose, 0.04% polysorbate 20, pH 5.8.

Atezolizumab will be delivered in infusion bags with IV infusion lines with product contacting surfaces of polyvinylchloride (PVC) and polyolefin and 0.2 μm in-line filters (filter membrane of polyethersulfone [PES]). No incompatibilities have been observed between v and PVC or polyolefin infusion materials (bags and infusion lines).

For further details, see the Atezolizumab Pharmacy Manual and IB.

Storage and handling

Atezolizumab must be refrigerated at 2°C-8°C (36°F-46°F) upon receipt until use. Atezolizumab vials should not be used beyond the expiration date provided by the manufacturer. No preservative is used in the Atezolizumab drug product; therefore, each vial is intended for single

use only. Vial contents should not be frozen or shaken and should be protected from direct sunlight.

Side Effects

Potential risks associated with Atezolizumab described here are based on observed nonclinical toxicities and adverse events observed in ongoing clinical trial(s) of Atezolizumab, as well as clinical toxicities related to monoclonal antibodies targeting the PD-L1/PD-1 pathway. Adverse events that have occurred within 24 hours after infusion include: infusion reactions, hypertension, fatigue, decreased appetite and headache.

Therapy with Atezolizumab may increase the risk of immune-related adverse events (IRAEs), including rash, hypothyroidism, hepatitis/transaminitis and colitis. Subjects should therefore be carefully monitored for evidence of clinically significant systemic IRAEs (e.g., SLE-like diseases) or organ-specific IRAEs (e.g., rash, colitis, uveitis, hepatitis, or thyroid disease).

Suggested workup for suspected IRAEs includes evaluation of the gastrointestinal tract, lung, liver, skin, eye, and pituitary and adrenal glands. Specific management of IRAEs is provided later in the protocol.

In addition, specific management for the toxicities occurring in the following organ systems is provided in this protocol: gastrointestinal tract (diarrhea, colitis), pulmonary (pneumonitis), hepato-biliary (hepatitis, pancreatitis), and dermatologic (rash, pruritus, severe cutaneous adverse reactions (SCARs)).

4.1.2 Tiragolumab

Classification

Tiragolumab is a fully human IgG1 monoclonal antibody. The recombinant antibody is produced in CHO cells, and consists of two heavy chains (456 amino acid residues each) and two light chains (220 amino acid residues each). There are two N-linked glycosylation sites (Asn306) in the Fc domain.

Mechanism of Action

Tiragolumab binds to TIGIT and prevents its interaction with Poliovirus receptor (PVR). The inhibitory immunoreceptor TIGIT has been shown to limit the effector function of tumor-associated lymphocytes.

Pharmacokinetics and Metabolism

Preliminary population-PK analyses show that tiragolumab exposures increased approximately dose-proportionally following IV administration at doses ranging from 100 to 1200 mg Q3W as monotherapy or in combination with 1200 mg Q3W atezolizumab. Preliminary population-PK analysis estimated tiragolumab clearance at 0.28 L/day with a linear drug elimination half-life of approximately 15 days.

Contraindications

Tiragolumab is contraindicated for patients with a history of severe allergic anaphylactic reactions to chimeric, human, humanized antibodies, or fusion proteins because of the potential for severe reactions.

Availability

The tiragolumab drug product will be supplied in single-use, 15-mL glass vials. The vials contain 10 mL of tiragolumab drug product and are buffered in histidine solution containing polysorbate 20, sucrose, L-methionine, and WFI. The approximate concentration of tiragolumab antibody in the vials is 60 mg/mL.

Storage and handling

The recommended storage condition for the tiragolumab drug product is 2°C-8°C (36°F–46°F). Do not shake or freeze IV bags containing dose solution. Protect from direct sunlight (exposure to indoor ambient light is acceptable).

Tiragolumab must be prepared for dosing under appropriate aseptic conditions as it does not contain antimicrobial preservatives. The dose solution should be used immediately. If not used immediately, the total storage time of the dose solution prior to administration should not exceed 24 hours to limit the risk of microbial growth in case of accidental contamination.

Side Effects

IRRs have been reported in patients treated with tiragolumab, with or without atezolizumab. The majority of events were mild to moderate and manageable. As an antagonist of TIGIT, tiragolumab is anticipated to enhance T-cell and NK cell proliferation, survival, and function. Therefore, tiragolumab may increase the risk of autoimmune inflammation (also described as immune-mediated AEs [imAEs]). In addition, due to the intact Fc-effector function of tiragolumab, lymphopenia via ADCC is a theoretical risk. For information on the pharmacokinetics, metabolism, formulation and handling of tiragolumab, see the pharmacy manual and the Tiragolumab Investigator's Brochure.

4.2 Accountability Records for Study Drug

The Investigational Pharmacist at each site will manage drug accountability records.

4.3 Ordering Study Drugs

UCSF will obtain Atezolizumab and Tiragolumab directly from Genentech as study supply. Drug will be shipped directly to subsites if required to ensure drug stability.

5 Treatment Plan

5.1 Dosage and Administration

Cohort A: The starting dose level of atezolizumab for Cohort A was 1200 mg administered by IV infusion on an outpatient basis for one dose, and was escalated in subsequent cohorts to 1200 mg administered by IV infusion every 3 weeks for a maximum of 3 neoadjuvant doses. Prior to Amendment 4.3 (October 19, 2020) subjects with adverse histology at the time of cystectomy (pT3, pT4, or N+) and no metastatic disease could elect to receive adjuvant MPDL3280A will receive 1200mg by IV infusion on an outpatient basis every 3 weeks for up to 16 doses cumulative doses.

Cohort B: The starting combination regimen will be atezolizumab 1200 mg administered by IV infusion on an outpatient basis every 3 weeks and tiragolumab 600 mg administered by IV infusion every 3 weeks for a total intended 3 neoadjuvant doses. As previously detailed, there will be a safety lead in of 6 initial patients at which time trial accrual will temporarily pause to assess the safety of combination treatment.

Administration of atezolizumab and tiragolumab will be performed in a setting with emergency medical facilities and staff who are trained to monitor for and respond to medical emergencies.

Atezolizumab and Tiragolumab will be delivered in infusion bags with IV infusion lines with product contacting surfaces of polyvinylchloride (PVC) and polyolefin and 0.2 μ m in-line filters (filter membrane of polyethersulfone [PES]). No incompatibilities have been observed between atezolizumab and PVC or polyolefin infusion materials (bags and infusion lines).

The compatibility of tiragolumab with diluents other than described is unknown. Tiragolumab must not be infused into the same line or cannula concomitantly with other drug infusions, including parenteral nutrition. Infusions of blood products and any electrolyte supplementation must not occur simultaneously with infusion of tiragolumab.

The initial dose of atezolizumab will be delivered over 60 (\pm 15) minutes. If the first infusion is tolerated without infusion-associated adverse events, the second infusion may be delivered over 30 (\pm 10) minutes. If the 30-minute infusion is well tolerated, all subsequent infusions (for subjects receiving more than 2 doses) may be delivered over 30 (\pm 10) minutes.

For the first infusion, the patient's vital signs (heart rate, respiratory rate, blood pressure, and temperature) should be determined within 60 minutes before, during (every 15 [\pm 5] minutes), and 30 (\pm 10) minutes after the infusion. For subsequent infusions, vital signs will be collected within 60 minutes before infusion, and during or after the infusion if clinically indicated or if symptoms occurred in the prior infusion. Patients will be informed about the possibility of delayed post-infusion symptoms and instructed to contact their study physician if they develop such symptoms.

No premedication will be allowed for the first dose of atezolizumab. Premedication may be administered for Cycles \geq 2 at the discretion of the treating physician after consultation with the Study Chair.

Tiragolumab dose will be administered following the dose of atezolizumab and will be delivered over 60 (\pm 15) minutes. If the first infusion is tolerated without infusion-associated adverse events, the second infusion may be delivered over 30 (\pm 10) minutes. If the 30-minute infusion is well tolerated, all subsequent infusions (for subjects receiving more than 2 doses) may be delivered over 30 (\pm 10) minutes.

For the first infusion, the patient's vital signs (heart rate, respiratory rate, blood pressure, and temperature) should be determined within 60 minutes before, during (every 15 [\pm 5] minutes), and 30 (\pm 10) minutes after the infusion. For subsequent infusions, vital signs will be collected within 60 minutes before infusion, and during or after the infusion if clinically indicated or if symptoms occurred in the prior infusion. Patients will be informed about the possibility of delayed post-infusion symptoms and instructed to contact their study physician if they develop such symptoms.

No premedication will be allowed for the first dose of tiragolumab. Premedication may be administered for Cycles ≥ 2 at the discretion of the treating physician after consultation with the Study Chair.

Table 5.1 Regimen Description

Study Drug	Premedication; precautions	Dose	Route	Schedule	Cycle Length
Atezolizumab	None for 1 st dose	1200mg	Intravenous	Day 1 each cycle	21 days
Tiragolumab (Cohort B only)	None for 1 st dose	600mg	Intravenous	Day 1 each cycle	21 days

5.1.1 Other Modalities or Procedures

A radical cystectomy per institutional standard of care is planned for all patients enrolling in this study. No other procedures following initiation of systemic treatment (e.g., TURBT) are required for subjects while on study. Cystectomy may be performed beginning 3 weeks after the last planned dose of study therapy is administered. See study calendar (Section 6.10) for schedule of evaluations.

5.2 Cohort A Multi-dose Schedule

Three successive cohorts were enrolled to evaluate immunologic impact of escalating neoadjuvant doses of atezolizumab prior to cystectomy as outlined in the table below. A fixed dose of atezolizumab 1200mg was given with each cycle. For individual subjects there was no dose modifications above or reductions below the assigned dose allowed.

Table 5.2 Cohort A Multi-Dose Cohort Schedule

Dose Level	Dose of Atezolizumab	Number of Patients Accrued Before Accrual of Next Cohort
1	1200 mg x 1 dose	6
2	1200 mg q3 weeks x 2 doses	6
3	1200 mg q3 weeks x 3 doses	6

Multi-dose cohort accrual then proceeded according to the following: Dosing began in the first cohort (Dosing Level 1) with atezolizumab 1200mg IV x 1 dose. Beginning with this starting dose level, six patients were treated at each cumulative dose level. Accrual to the next higher

dose cohort began after 6 subjects in the lower cohort completed treatment and underwent cystectomy.

18 patients were treated in this multi-dose phase.

Cohort A Dose-expansion occurred at dose level 3 given no unacceptable treatment-related toxicity (as defined in Section 5.4) was observed. The rationale for expansion at this dose level is discussed in Section 1.8.

5.3 Cohort B Safety Lead-in Schedule

The Cohort B safety lead-in is described in section 3.1. Dosing for the Cohort B safety lead-in is detailed below. Once the intended treatment regimen is established following completion of the safety assessment, an additional 15 patients will be enrolled at the same regimen for a total of 21 patients on that treatment regimen.

Table 5.3 Cohort B Safety Lead-in Dosing

Dose Level	Atezolizumab	Tiragolumab
1	1200 mg q3 weeks x 3 doses	600mg x 3 doses
2	1200 mg q3 weeks x 3 doses	600mg x 2 doses
3	1200 mg q3 weeks x 3 doses	600mg x 1 dose

5.4 Dose Limiting Toxicities (DLTs)

Dose Limiting Toxicity (DLT) is an unacceptable treatment-related toxicity that occurs between time of first dose and time of cystectomy, defined as:

- any Grade 4 toxicity, or
- any recurrent Grade 3 toxicity, or
- any Grade 3 toxicity persisting more than 2 weeks, or
- any toxicity that results in delay of cystectomy beyond 12 weeks from the first dose of study drug

5.5 Interim Safety Analysis

A stopping rule for safety will halt accrual to the study and prompt reevaluation of the treatment regimen if unacceptable treatment-related toxicity (defined as any Grade 4 toxicity, any recurrent Grade 3 toxicity, or any Grade 3 toxicity persisting more than 2 weeks), or treatment-related delay in cystectomy beyond 12 weeks (12 week window starts at time of first dose to time of cystectomy), is observed at a frequency of $\geq 33.3\%$.

Because of the known excellent safety profile of atezolizumab, this safety review will occur after all 6 subjects have been accrued to each individual dosing cohort in the Cohort A multi-dose phase and Cohort B safety lead-in and treated with at least one dose of study treatment, as well as on an ongoing basis should serious treatment-related toxicities or treatment-related delays in cystectomy be observed at any point in the study.

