 - **Dose Level 1** (Atezolizumab 1200 mg x 3 cycles, Tiragolumab 600 mg x 3 cycles): There will be an initial safety lead in of 6 patients treated with this regimen, at which time enrollment will pause to assess the safety of this combination treatment. As long as no more than 1 out of the initial 6 patients experience dose limiting toxicities (DLTs) or a delay in the time to radical cystectomy, the remaining patients will enroll at the same dose and regimen.
 - If two or more patients out of the initial six experience DLTs within the first cycle (3 weeks), accrual will be halted and the combination reevaluated.
 - If two or more patients out of the initial six experience DLTs within the first 2 cycles (6 weeks), accrual to this dose level will be halted and we will move to dose level 3.
 - If two or more patients out of the initial six experience DLTs or delay in the time to radical cystectomy, and no more than 1 patient experienced DLTs during the first 2 cycles (6 weeks), the next six patients will be treated at dose level 2
 - **Dose Level 2** (Atezolizumab 1200 mg x 3 cycles, Tiragolumab 600 mg x 2 cycles): As long as no more than 1 out of 6 patients experience DLTs or a delay in the time to radical cystectomy with this treatment, the remaining patients will enroll at the same dose and regimen.
 - If two or more patients out of the six patients experience DLTs within the first cycle (3 weeks), accrual will be halted and the combination reevaluated.
 - If two or more patients out of the six experience DLTs or delay in the time to radical cystectomy, and no more than 1 patient experienced DLTs during the first cycle (3 weeks), the next six patients will be treated at dose level 3
 - **Dose Level 3** (Atezolizumab 1200 mg x 3 cycles, Tiragolumab 600 mg x 1 cycle): This will be the selected regimen if no more than 1 out of 6 patients experience DLTs or a delay in the time to radical cystectomy. However if 2 or more patients experience DLTs or a delay in the time to radical cystectomy with this combination regimen, then accrual will be halted and the combination reevaluated.
- Expansion: Once the intended treatment regimen is established following completion of the safety assessment, an additional 15 patients will be enrolled at the same regimen for a total of 21 patients on that treatment regimen.

Cohort B Safety Lead-in Schema

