8.2 Interim Analyses and Stopping Rules

A stopping rule for safety will halt accrual to the study and prompt reevaluation of the regimen if unacceptable treatment-related toxicity (defined as any Grade 4 toxicity, any recurrent Grade 3 toxicity, or any Grade 3 toxicity persisting more than 2 weeks), or treatment-related delay in cystectomy beyond 12 weeks (including both the treatment period and any delay due to an adverse event), is observed at a frequency of $\geq 33.3\%$

No formal interim stopping rule for efficacy will be performed. This is due to the fact that immune therapies may require weeks to months to have efficacy, and therefore the true antitumor activity of atezolizumab and tiragolumab may not be apparent at the time of cystectomy. Rather, durable immune responses may be generated against the tumor and may prevent post-cystectomy recurrence; this effect may not be detectable for months to years after study drug administration.

Furthermore, given the relatively small sample size of this study an interim stopping rule for futility based on longer-term clinical endpoints (i.e. relapse-free survival) is not considered feasible or warranted.

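### The Cohort B lead-in review is timed from the first dose, while its pass criterion runs to cystectomy, and no text makes expansion wait for surgical outcomes

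*Combined protocol and SAP*

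**What the plan says.** **Review point.** Section 5.5 times the review for when all six patients have entered each dosing group of the "Cohort B safety lead-in and treated with at least one dose of study treatment". It adds ongoing review if serious treatment-related toxicity or surgical delay is seen at any time. In Appendix 2 the Study Chair's report and request to proceed come after lead-in enrolment is complete, and the DSMC audits lead-in visits through cycle 1. The same appendix lists DSMC review of all lead-in participant data. It also requires the report to cover protocol-defined DLTs and lets the DSMC ask for more information.

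**Criterion.** Section 3.1 pauses enrolment after six patients and keeps dose level 1 provided that "no more than 1 out of the initial 6 patients experience dose limiting toxicities (DLTs) or a delay in the time to radical cystectomy". Under 5.4 a DLT "is an unacceptable treatment-related toxicity that occurs between time of first dose and time of cystectomy", and the definition includes toxicity that pushes surgery past 12 weeks from first dose.

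**Action at the boundary.** Section 5.5 states: "A stopping rule for safety will halt accrual to the study and prompt reevaluation of the treatment regimen", at a frequency of 33.3% or more. Section 8.2 repeats the rule. In 3.1, two or more events of six can instead lead to a step-down. From level 1, "accrual to this dose level will be halted and we will move to dose level 3", or "the next six patients will be treated at dose level 2"; from level 2, "the next six patients will be treated at dose level 3".

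**Cohort A.** Section 5.2 records that the next dose level opened only after six patients at the lower level had finished treatment and had surgery.

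**The concern.** A review at one dose cannot judge a criterion that ends at surgery. Surgical delay, the component specific to this neoadjuvant setting, is the part least visible at that point. The branches in 3.1 also need data to week 3, week 6 and surgery before a lead-in can be assigned to one of them. If expansion is authorised at the stated review point, curative-intent patients can be enrolled on a regimen that then fails its own rule. Section 5.5 justifies its schedule by the known safety of atezolizumab, whereas this lead-in exists to test the addition of tiragolumab.

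**Working it through.** **The plan's own figure.** 2/6 = 33.3%, so the halt frequency in 5.5 and 8.2 and the failure boundary in 3.1 are the same count in a group of six.

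**When the criterion is complete.** There are three doses three weeks apart (weeks 0, 3 and 6), with surgery from three weeks after the last planned dose (5.1.1). The earliest on-schedule surgery is therefore week 9, and the window closes at week 12.

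**Follow-up at the stated review point.** Section 3.6 gives 11-16 months to accrue Cohort B. I assume 21 patients, even accrual, no pause and 4.348 weeks per month.
- 11 months: spacing 11 × 4.348 / 21 = 2.28 weeks. At patient 6's first dose, follow-up is 11.4, 9.1, 6.8, 4.6, 2.3 and 0 weeks. Two of six have reached week 9 and none week 12.
- 16 months: spacing 16 × 4.348 / 21 = 3.31 weeks. Follow-up is 16.6, 13.3, 9.9, 6.6, 3.3 and 0 weeks. Three have reached week 9 and two week 12.

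**Lead-ins that look clean and later fail.** Let p be the true probability of a qualifying event by cystectomy, and F(t) the share of events that have appeared by week t. The documents give no F, so I use three assumptions: uniform over 12 weeks (F = t/12), and one third or one half of events in cycle 1 with the rest even to week 12. With T events in total and S seen at review,

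P(S ≤ 1 and T ≥ 2) = P(T ≥ 2) − P(S ≥ 2),

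where patient i contributes to S with probability p·F(t_i).

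P(T ≥ 2) = 1 − (1−p)^6 − 6p(1−p)^5 = 0.114, 0.345 and 0.649 at p = 10%, 20% and 1/3.

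Worked case (p = 1/3, 2.28-week spacing, uniform):
- The seen probabilities are 0.316, 0.253, 0.190, 0.127, 0.063 and 0.
- P(S = 0) = 0.684 × 0.747 × 0.810 × 0.873 × 0.937 = 0.339.
- P(S = 1) = 0.422, so P(S ≥ 2) = 0.239.
- The result is 0.649 − 0.239 = 0.410.

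Ranges over the three event-time assumptions:

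| Review point | Spacing (weeks) | p = 10% | p = 20% | p = 1/3 |
|---|---|---|---|---|
| Patient 6, first dose | 2.28 | 0.073-0.087 | 0.200-0.245 | 0.319-0.410 |
| Patient 6, first dose | 3.31 | 0.058-0.069 | 0.154-0.189 | 0.231-0.294 |
| Patient 6, end of cycle 1 | 2.28 | 0.039-0.056 | 0.101-0.151 | 0.147-0.229 |
| Patient 6, end of cycle 1 | 3.31 | 0.030-0.044 | 0.078-0.116 | 0.110-0.169 |

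Overall this is about 6-9%, 15-25% and 23-41% at first dose, and 3-6%, 8-15% and 11-23% after cycle 1.

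**Patients exposed.** All six reach week 12 within 12 weeks of patient 6's first dose. In that time 12/2.28 = 5.3 or 12/3.31 = 3.6 further patients arrive, so about 3 to 5 could be enrolled.

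**Counting in expansion.** After 1/6 in the lead-in, two events in the first six expansion patients is 2/6 = 33.3% if expansion is counted alone, but 3/12 = 25% per regimen.

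**The case against.** The best reply is that 5.5 is not the gate to expansion. Its review sentence covers both cohorts in the same words, and in Cohort A it coexisted with a later gate in 5.2. It can be read as a minimum, not a decision date. For Cohort B, 3.1 pauses enrolment, applies a criterion that cannot be settled after one dose, and opens expansion only when the safety assessment is complete. Appendix 2 has the DSMC review all lead-in data and receive DLTs as the protocol defines them, and those run to surgery. The cycle 1 sentence concerns visit auditing. The Cohort B schema figure was not available to me and may say more.

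Much of this stands: a careful team could reach the right practice. It does not remove the conflict. The only stated time points are one dose and completion of enrolment, and Cohort B has no counterpart to the surgical condition in 5.2. Ongoing review acts on a late event only after it occurs.

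Three stronger readings are tempting, and the documents do not support them.
- **All 15 expansion patients would be treated on a failing regimen.** Lead-in outcomes are complete within 12 weeks of patient 6's first dose, and a second event breaks the 3.1 condition and prompts the 5.5 review.
- **Sections 3.1 and 5.5 contradict each other at 2 of 6.** Reevaluating a regimen is compatible with stepping down, 5.3 defers to 3.1, and 1.8 foresees fewer tiragolumab doses. What is missing is a sentence saying so.
- **The expansion rule cannot be applied without a stated denominator.** Both 5.5 and 8.2 speak of the regimen, and 8.3.2.2 summarises adverse events by regimen, so per-regimen counting is the natural reading.

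A reader might also compute larger probabilities by deducting a 12-week pause from accrual time, which gives 1.71-week spacing and 8-10%, 24-29% and 40-50%. That is inconsistent: it shortens the spacing for a pause that the early review is then assumed not to observe.

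**Conclusion.** The timing conflict holds and should be fixed. The stated review point precedes completion of the criterion for at least three of the six patients under the accrual assumed here, taking week 9 as the earliest completion. The probabilities rest on even accrual of 21 patients, no pause and assumed event-time curves, none of which the protocol gives. Surgical delays that become known only at week 12 would come later than these curves allow and would raise the figures. If the team already holds expansion until surgery under 3.1, nothing is missed and the defect is one of wording. The relation of the 33.3% halt to the step-downs, and the expansion denominator, are clarifications only.

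**What to change.** In 5.5 and Appendix 2, authorise expansion only after all six patients at that dose level have had cystectomy or reached 12 weeks from first dose. Act at once when a second event occurs, without waiting for the rest.

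As accompanying clarification in 5.5 and 8.2, state that the 3.1 branches govern during the lead-in when 2 of 6 meets the 33.3% halt. State also that in expansion the 33.3% is counted per regimen, including its six lead-in patients.

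The cost is amendment wording plus a pause of up to about 9-12 weeks from the sixth patient's first dose at each level used. If all three levels were needed, that is 27-36 weeks (6.2-8.3 months at 4.348 weeks per month), against 11-16 months of planned accrual. There is no added time if surgical outcomes are already awaited under 3.1.
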